## INTRODUCTION

Shoulder osteoarthritis is a common and important health problem. Degenerative changes in this joint affect the tendon system of the rotator cuff, the articular cartilage of the humerus and the long tendon of the biceps and constitute one of the main causes of incapacity for work. For patients, it is a health problem comparable in their perception of illness to heart failure or diabetes.

Shoulder prosthesis, shoulder arthroplasty or prosthetic shoulder replacement is a surgical procedure in which the glenohumeral joint (the joint between the head of the humerus and the scapula) is replaced by a prosthetic implant. This procedure is indicated primarily in cases of advanced osteoarthritis or severe shoulder arthritis (as in rheumatoid arthritis) to control pain and regain lost function; and also after some proximal shoulder fractures in which surgical reconstruction is not possible. (Reverse total shoulder arthroplasty for irreparable rotator cuff tears and cuff tear arthropathy. Ramirez MA, Ramirez J, Murthi AM. Clin Sports Med. 2012 Oct;31(4):749-59. doi: 10.1016/j.csm.2012.07.009.) Review)

The anatomical shoulder prosthesis reproduces the natural anatomy of the shoulder. For proper function it requires that the tendon apparatus of the shoulder be preserved.

In the reverse shoulder prosthesis the humerus articulates over the scapular component, in this case hemispherical, in reverse of the natural arrangement of the joint. Reverse replacement allows the deltoid muscle to be used to perform shoulder function by dispensing with the tendons that constitute the rotator cuff, (Walker M1, Brooks J, Willis M, Frankle M. How reverse shoulder arthroplasty works. Relat Res. 2011 Sep;469(9):2440-51. doi: 10.1007/s11999-011-1892-0) .

It consists of several components: the humeral stem, the insert which is usually made of polyethylene and is implanted in the metaphyseal area of the humeral component,

Prospective randomized clinical study to analyze the functional, radiological and strength results in lateralized and medialized models of reverse shoulder arthroplasty.

#### Shoulder and Elbow Unit

the metaglenoid which is the component of the prosthesis that after milling the glenoid bone is implanted on the native glenoid by screwing it, and the glenosphere which would correspond to the humeral head and which in turn is fixed to the metaglenoid by means of a screw (figure 1).

[figure not shown]

Figure 1- Components of the Reverse Arthroplasty: A: Stem, B: Insert, C: Glenosphere, D: metaglenoid, E: Screws.

This is very useful in patients who have irreparable damage to the shoulder tendons that form part of the rotator cuff, as occurs in a large part of the elderly population. Some of these patients have a serious functional alteration called "pseudoparalytic shoulder", in which they can hardly move their arm; for this situation there were no successful treatments until the appearance of the inverted prostheses. the appearance of inverted prostheses; now, thanks to them, patients can recover adequate function in a fairly reproducible manner.

Since the appearance of the first inverted prosthesis designs, important design modifications have appeared in order to reduce or avoid complications and improve functional results (Kazley JM, Cole KP, Desai KJ, Zonshayn S, Morse AS, Banerjee S. Prostheses for reverse total shoulder arthroplasty. Expert Rev Med Devices. 2019;16(2):107-118. doi:10.1080/17434440.2019.1568237),

Similarly, the expansion of its indications (initially only used in rotator cuff arthropathies as etiology and later its use was extended to other etiologies such as

Prospective randomized clinical study to analyze the functional, radiological and strength results in lateralized and medialized models of reverse shoulder arthroplasty. Shoulder and Elbow Unit massive ruptures, primary glenohumeral arthrosis, fractures or tumors) has influenced the emergence of different prosthetic models.

Currently we can classify the inverted arthroplasty according to the characteristics of the components (glenosphere, humeral component or both).

However, medialized models also have their advantages. Theoretically the forces to which the gleno-metaglenoid interface is subjected are lower which would decrease the risk of disimplantation by improving the initial fixation (Roche CP, Stroud NJ, Flurin PH, et al Reverse shoulder glenoid baseplate fixation: a comparison of flat---back versus curved-back designs and oval versus circular designs with 2 different offset glenospheres. *J Shoulder Elbow Surg*. 2014 Sep;23(9):1388-94) (Stroud N, DiPaola MJ, Flurin PH, Roche CP. Reverse shoulder glenoid loosening: an evaluation of the initial fixation associated with six different reverse shoulder designs. *Bull Hosp Jt Dis* (2013). 2013;71 Suppl 2:S12-7)

Lateralized models, although so named because their CoR is more lateral than that of medialized models, are also medialized with respect to the anatomical situation. But as the thickness of the glenosphere is at least 5 mm more than its spherical radius, the

Prospective randomized clinical study to analyze the functional, radiological and strength results in lateralized and medialized models of reverse shoulder arthroplasty. Shoulder and Elbow Unit

center of rotation is lateral to the glenoid surface. This lateral displacement would decrease the deltoid abduction moment relative to medialized designs but would be superior relative to the anatomic situation (Henninger HB, Barg A, Anderson AE, et al. Effect of lateral offset center of rotation in reverse total shoulder arthroplasty: a biomechanical study. J Shoulder Elbow Surg. 2012 Sep;21(9):1128-35) (Hamilton MA, Roche CP, Diep P, et al.

Effect of prosthesis design on muscle length and moment arms in reverse total shoulder arthroplasty. Bull Hosp Jt Dis (2013). 2013;71 Suppl 2:S31-5). For this reason lateralized designs are associated with less efficient of the deltoid than medialized ones being the force required by the deltoid to elevate the arm greater with a lateralized model than a medialized model which theoretically could have implications on the maximal range of motion achieved postoperatively, in achieving stable fixation to the glenoid, and in the rate of acromion stress fractures (due to shear forces generated by the deltoid) (Henninger HB, Barg A, Anderson AE, et al. Effect of lateral offset center of rotation in reverse total shoulder arthroplasty: a biomechanical study. J Shoulder Elbow Surg. 2012 Sep;21(9):1128- 35) (Hamilton MA, Roche CP, Diep P, et al. Effect of prosthesis design on muscle length and moment arms in reverse total shoulder arthroplasty. Bull Hosp Jt Dis (2013). 2013;71 Suppl 2:S31-5)(Levy JC, Anderson C, Samson A. Classification of postoperative acromial fractures following reverse shoulder arthroplasty. J Bone Joint Surg Am. 2013 Aug 7;95(15):e104). However, the lateralized models do stress the residual rotator cuff better, which theoretically improves internal and external rotations with respect to medialized models that do not act at the humeral level (Roche et al).

Lateralized designs also increase the deltoid wraparound effect relative to lateralized designs which increases horizontal compression forces increasing prosthetic stability (Roche et al). Finally, these designs appear to have lower rates of scapular notching.

[figure not shown]

Figure 1- Medialized and lateralized glenospheres. Source: Own elaboration

Prospective randomized clinical study to analyze the functional, radiological and strength results in lateralized and medialized models of reverse shoulder arthroplasty. Shoulder and Elbow Unit

For the humeral component, each prosthetic model also presents variations in its characteristics. For its understanding, it is necessary to define the concept of humeral offset, which refers to the horizontal distance between the intramedullary canal and the humeral stem axis at the center of the insert. In turn, the metaphyseal component of the prosthesis can be sunk in the bone (Onlay prosthesis or on the Inlay bone) - Figure 2.

[figure not shown]

Figure 2. Medialization and lateralization of the humeral component with Inlay and Onlay humeral component respectively.

A humeral component with an offset of 15 mm or less is considered a medialized humerus and one with an offset greater than 15 mm is considered lateralized. The offset determines the amount of lateralization of the humerus and is influenced by the cervico-diaphyseal angle. The humeral osteotomy, and the use of stems with the proximal part sunk or not in the bone, when not sunk the tray that rests on the superior humeral cortex can be lateralized or not.

The medialized designs are traditionally Inlay (i.e. sunken proximal part) and with a non-anatomic 155° osteotomy. Doing so distalizes the humerus in relation to its anatomical situation and increases the tension on the deltoid. With these medialized humerus designs, the deltoid is lengthened, the enveloping effect of the deltoid is diminished and therefore the compressive forces are reduced. This results in little

Prospective randomized clinical study to analyze the functional, radiological and strength results in lateralized and medialized models of reverse shoulder arthroplasty. Shoulder and Elbow Unit

improvement in the deltoid lever arm. In addition, the medialization of the humerus also moves the residual rotator cuff insertion, shortening its length, which can have its length, which can have negative implications for rotations.

Finally, both components can be combined, although understanding the influence of each component on the biomechanical behavior of the reverse arthroplasty is important, the impact of the combination of both is essential. The combination of humeral components and medialized glenospheres accentuates all the negative aspects of medialization and forces subscapularis tendon repair for maintenance of prosthetic stability. (Edwards TB, Williams MD, Labriola JE, et al. Subscapularis insufficiency and the risk of shoulder dislocation after reverse shoulder arthroplasty. J Shoulder Elbow Surg. 2009 Nov- Dec;18(6):892-6) (Routman HD. The role of subscapularis repair in reverse total shoulder arthroplasty. Bull Hosp Jt Dis (2013). 2013;71 Suppl 2:108-12). The medialized models also in the case of native glenoid erosion due to existing pathology cannot correct the existing deformity requiring bone grafts to lateralize the glenosphere.

When we lateralize the glenosphere and leave the humeral component medialized, the deltoid wrapping effect improves, improves the recruitment of the residual rotators and improves the stability of the implant, and the repair of the subscapularis tendon

Prospective randomized clinical study to analyze the functional, radiological and strength results in lateralized and medialized models of reverse shoulder arthroplasty. Shoulder and Elbow Unit

can be dispensed with. However, the deltoid lever arm is less than when the glenosphere is medialized and the humeral component lateralized due to the greater lateralization of the center of rotation. (Henninger HB, Barg A, Anderson AE, et al.

Effect of lateral offset center of rotation in reverse total shoulder arthroplasty: a biomechanical study. J Shoulder Elbow Surg. 2012 Sep;21(9):1128- 35) (Hamilton MA, Roche CP, Diep P, et al. Effect of prosthesis design on muscle length and moment arms in reverse total shoulder arthroplasty.

## JUSTIFICATION

Inverted arthroplasty began to be used at the Hospital Clínico San Carlos in 2008. The model used since then has been a model with medialization of the center of rotation. In the last year a new implant with lateralization of the center of rotation has been introduced and approved by the center for the same indications. The learning curve for the implantation of a reverse arthroplasty has been estimated at 7 cases for one shoulder surgeon (Wierks C et al Reverse shoulder replacement: intraoperative and early postoperative complications. Clin Orthop Relat Res. 2009 Jan;467 (1):225-34) and is therefore considered outdated given that 12 such arthroplasties have been performed.

The absence of prospective randomized clinical studies that compare models with medialization of the center of rotation with those with lateralization of the center of rotation has led us to propose the present study in order to determine if there are differences in relation to function or strength between the two implants.

Prospective randomized clinical study to analyze the functional, radiological and strength results in lateralized and medialized models of reverse shoulder arthroplasty. Shoulder and Elbow Unit

#### THEORETICAL BASIS

As explained in the introduction, several biomechanical studies have analyzed theoretically the function and possible functional repercussions of each prosthetic model (medialized vs. lateralized). There are studies that publish the functional results of each prosthetic model separately. However, there are no prospective randomized clinical studies that analyze the functional outcomes (range of motion and strength) and complications with each type of implant in a homogeneous population.

Determining whether the type of implant has any influence on these outcomes is essential to maximize functionality and decrease the number of complications, which would additionally imply a decrease in health and social costs for the patient.

Therefore, our null hypothesis is that the use of implants with lateralization of the center of rotation does not offer superior clinical results compared to the use of medialized implants. medialized implants. The alternative hypothesis is that the use of lateralized implants offers superior clinical results compared to medialized implants.

#### OBJECTIVE

The objective of this study is to determine the functional results (range of motion) and strength as well as the percentage of complications that appear with the use of two inverted arthroplasty systems (one medialized and the other lateralized).

In the treatment of rotator cuff arthropathies or irreparable cuff tears.

#### INCLUSION CRITERIA

The inclusion criteria are as follows:

-Male or female patients over 65 years of age with rotator cuff arthropathy refractory to conservative treatment after six months.

-Ability to understand the Information Sheet, the Informed Consent and the evaluation scales.

#### EXCLUSION CRITERIA

The following will be excluded from the present study:

-Patients who do not grant their Consent.

-Patients with sequelae of fractures, rheumatoid arthritis, avascular necrosis, previous infectious processes, primary glenohumeral arthrosis, revision surgeries that have required conversion to an ITHA.

-Patients in whom another surgical procedure has been associated with ITHA, such as tendon transfer.

Prospective randomized clinical study to analyze the functional, radiological and strength results in lateralized and medialized models of reverse shoulder arthroplasty. Shoulder and Elbow Unit

-Glenoid bone defects in the horizontal plane (types B2 and C of Walch's classification  
Walch G, Badet R, Boulahia A, Khouri A. Morphologic study of the glenoid in primary  
glenohumeral osteoarthritis. J Arthroplasty 1999; 14:756-60)

-In the horizontal plane (types B2 and C of the Walch classification Walch G, Badet R,  
Boulahia A, Khouri A. Morphologic study of the glenoid in primary glenohumeral  
osteoarthritis. J Arthroplasty 1999; 14:756-60) or in the vertical plane ( Sirveaux stages  
E3) Sirveaux F, Favard L, Oudet D, Huquet D, Walch G, Molle D. Grammont  
inverted total shoulder arthroplasty in the treatment of glenohumeral osteoarthritis  
with massive rupture of the cuff. Results of a multicentre study of 80 shoulders. J Bone  
Joint Surg Br 2004;86: 388-95) requiring bone supplementation or augmented  
metaglens.

-Patients who have previously undergone surgery on the affected limb.

-Inability to understand the information sheet, informed consent, and  
The evaluation scales.

#### WITHDRAWAL CRITERIA

Patients will be withdrawn if, after having accepted the consent, they freely decide to  
abandon the study or if they present an adverse event.  
adverse event.

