#### PRIMARY AND SECONDARY VARIABLES

The primary objective will be to compare functional outcomes (Constant scale score)  
24 months after surgery in patients over 65 years of age with cuff arthropathies  
treated with either of the two options: medialized ITHA or lateralized ITHA, then the  
results obtained on the Constant scale at 24 m will be the variable of choice.

Constant scale at 24 m will be the primary variable. Secondary variables will include:  
visual analogue pain scale (VAS) and Quick-DASH and ASES questionnaires for  
functionality, range of motion, strength.

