#### Statistical analysis

A descriptive analysis of the variables under study will be performed. The description of quantitative variables such as age, Charlson comorbidity index, questionnaires for the assessment of functionality (Constant, Quick-DASH, ASES), VAS and RHB sessions, will be carried out using the mean and standard deviation.

Categorical variables such as affected and dominant limb or satisfaction will be described by frequency and percentage. The normality of the available data will be checked using the Kolmogorov-Smirnov test.

To determine that both groups are similar, the Student's t-test will be used for continuous variables such as age, Charlson index and RHB sessions, while for categorical variables (dominant and affected limb and sex) the Pearson's chi-square test or Fisher's exact test will be used, depending on the characteristics of the variables.

Once the characteristics of the groups have been described, comparisons will be made between the two interventions (medialized IHTA and lateralized IHTA) in the main study variables. To determine whether there are statistically significant differences in

Prospective randomized clinical study to analyze the functional, radiological and strength results in lateralized and medialized models of reverse shoulder arthroplasty. Shoulder and Elbow Unit  
the Constant scale at 24 months between the two procedures, a general linear model will be performed. The same analysis will be used with the quick-DASH and ASES questionnaire.

For the analysis of strength during movement, VAS, as well as the rest of the questionnaires (including the standardized or age- and sex-adjusted Constant and the subsections of this questionnaire) at the different evaluation times of the study (1, 3, 6, 12, 18 and 24 months), the Student's t-test will be used. To compare the complications that occurred in both groups, Pearson's Chi-squared test will be used. Similarly, Pearson's Chi-square test will be used to compare satisfaction with what happened in each group.

Finally, to establish the existence of a relationship between Constant and normalized Constant and patient satisfaction, Pearson's correlation will be used. The results of the statistical tests will be given with a confidence level of 95%; that is, statistical significance will be set at 0.05. The statistical study will be performed using the IBM SPSS program (v.25).

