Three weeks after surgery, new X-rays will be taken in three planes and referral to the Rehabilitation Center to begin active mobility, strengthening and gaining joint balance.

Visits 4, 5, 6 and 7: Groups 1 and 2. Three, Six, Twelve and 24 months after surgery.

Radiographic evaluation at each visit including the same three projections.

Clinical evaluation by means of the above mentioned scales and measurement of the BA to assess the functionality of the shoulder.

Finally in this phase, at the end of the follow-up of both groups (24 months), a cost analysis is performed by measuring direct costs (hospital stay, operating room costs, imaging tests, outpatient consultations, physiotherapy sessions, emergency visits, transport, medication consumption, etc.), medication consumption...) and indirect costs (need for home help, family leave...) and an isokinetic study of the shoulder (strength and mobility).

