## • PERIOD OF STUDY

PERIOD OF STUDY							
	Recruitment :	Randomization	Post-randomization				Closure
Starting point	-1	0	0w	1 W	1 M	6M	12 M
Recruitment:							
SelectionPatients		X					
Informed consent		X					
Randomization		X					
Interventions							
Lateralized RSA			X				
Medialized RSA			X				
AssessmentDemographic and epidemiological data, Constant, ASES, Quick Dash, VAS, RAM, Strength, Radiological		X					
			X				

Prospective randomized clinical study to analyze the functional, radiological and strength results in lateralized and medialized models of reverse shoulder arthroplasty.  
Shoulder and Elbow Unit

Adverse events		x	x	x	x	x	x	x
----------------	--	---	---	---	---	---	---	---

Study protocol. Diagram according to recommendations for intervention studies (SPIRIT).

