#### ETHICAL ASSURANCE. RISKS AND BENEFITS.

The surgical procedure, follow-up and treatment of the patients operated by inverted arthroplasty with any of the two implants will be done in the same way as it is currently done in patients treated with these prosthetic systems and who are not included in any study.

Participation in this study does NOT carry any additional risk to the risks inherent to the operation to which the patient will be subjected. These risks inherent to the operation and which are NOT derived from the study are duly included in the Informed Consent for Surgical Intervention.

The participation of the patients in the study does NOT imply any additional cost (neither for the institution nor for the patient) directly related to the participation in the study. All procedures performed on patients participating in the study are those routinely performed on all patients treated by the shoulder unit in whom a reverse prosthesis has been implanted.

The procedure to be adopted to protect the identity and confidentiality of the data generated by the research complies with the Organic Law on Personal Data Protection (Law 3/2018). All data will be collected confidentially after assignment of a file number, avoiding nominal identification, with health labels and even initials. No patient will be personally identified in any report or publication resulting from this study. The study protocol proposed to you has been drafted in accordance with the Standards of Good with the European Union Standards of Good Clinical Practice and the current revision of the Helsinki Declaration.

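### Withdrawing every patient who has an adverse event, with no rule for later data, can leave the 24-month Constant comparison resting on event-free patients

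*Combined protocol and SAP*

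**What the plan says.** The Withdrawal Criteria section gives two grounds for mandatory withdrawal after consent: the patient chooses to leave, or has an adverse event. In its words, patients are withdrawn if they "abandon the study or if they present an adverse event". Severity, relatedness and timing are not qualified, and adverse event is not defined.

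The primary endpoint is fixed in Primary and Secondary Variables: "Constant scale at 24 m will be the primary variable". The Statistical Analysis section compares "the Constant scale at 24 months between the two procedures, a general linear model". It names no analysis population, missing-data method or sensitivity analysis. The sample-size paragraph inflates the number of patients for a 20% loss rate and does not say whether adverse-event withdrawals are part of that 20%.

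Other sections assume that events are observed and counted:

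- The Objective section includes the percentage of complications with each implant.
- The Procedure section records complications during surgery and immediately afterwards.
- The Statistical Analysis section specifies a chi-squared test "To compare the complications that occurred in both groups".
- The Period of Study table marks "Adverse events" across its time points.

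On follow-up, the Ethical Assurance section says that "All procedures performed on patients participating in the study are those routinely performed on all patients treated by the shoulder unit" receiving a reverse prosthesis.

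**The concern.** The intervention is a single operation, so withdrawal cannot sensibly mean stopping treatment. Paired with a decision to abandon the study, it means leaving the study. A patient withdrawn for a complication would then have no 24-month Constant score as study data, and the general linear model would be fitted to those who had no event. This last step is an inference, because the plan does not say in words that such patients are excluded.

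The Introduction gives reasons, with qualifiers, why complications may differ by implant. It mentions dislocation with medialised designs if nothing is done on the humeral side and, in theory, acromial stress fracture with lateralised designs. If the implant affects who is withdrawn, the patients left in each arm are no longer comparable by randomisation, and the arm that loses more to complications looks better than it should.

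The complication comparison also suffers. The event that triggers withdrawal can still be counted, but later complications in the same patient may not be. Scores that are not collected at 24 months cannot be recovered afterwards.

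**Working it through.** **Plan figures used.** 17 per group before and 21 per group after the loss allowance; 20% loss; type I error 0.05; power 80%; target difference 10 Constant points; minimal clinically important difference 8 points (all from the sample-size paragraph). No standard deviation, event rate or score loss is given.

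**The plan's own figure.** 17 × 1.2 = 20.4, rounded up to 21 per group or 42 in total, which matches the stated final number. Dividing instead gives 17 / 0.8 = 21.25, or 22 per group. The base of 17 cannot be verified without a standard deviation. Under a two-sided normal approximation it implies about 10.1 to 10.4, and under a t-test about 9.8 to 10.1. An SD of 10 is assumed below.

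**Bias.** Let p be the event risk in an arm and d the mean loss in 24-month Constant score among patients with an event. An arm's all-randomised mean lies p × d below its event-free mean. Restricting to event-free patients therefore shifts the difference between arms A and B by

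shift = pA × dA − pB × dB, in favour of A when positive.

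All risks and losses below are assumptions.

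| Arm A (risk, loss) | Arm B (risk, loss) | Shift towards A |
|---|---|---|
| 20%, 10 | 10%, 10 | 2 − 1 = 1 |
| 30%, 20 | 10%, 20 | 6 − 2 = 4 |
| 20%, 20 | 20%, 10 | 4 − 2 = 2 |
| 30%, 10 | 10%, 20 | 3 − 2 = 1 |
| 20%, 20 | 20%, 20 | 4 − 4 = 0 |

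The product of risk and loss decides the direction; neither does so alone. A simulation with 1,000,000 patients per arm and equal event-free means agrees: the all-randomised differences were 1, 4, 2, 1 and 0 points against A, and the event-free difference was about 0 each time. With a loss of 30 points and risks of 30% and 10%, the shift would be 9 − 3 = 6.

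**Numbers withdrawn.** At event risks of 10%, 20% and 30%, 21 × risk = 2.1, 4.2 and 6.3 patients per arm. If the loss allowance is read as 21 − 17 = 4 per arm, a 20% event risk uses all of it before any other loss.

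**Effect on power of keeping everyone.** Retained patients with events widen the spread: SD = √(100 + p(1 − p)d²). With p = 0.2 in both arms and 17 evaluable per arm, two-sided 0.05, true difference 10 points:

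- Loss 20: √(100 + 0.16 × 400) = 12.8. Power is about 62% by normal approximation and 60% by t-test.
- Loss 10: √(100 + 0.16 × 100) = 10.8. Power is about 77% and 75%.
- No events, SD 10: 83% and 81%.
- Event patients withdrawn: about 17 × 0.8 = 13.6 remain. Simulated t-test power is about 70%, for the event-free difference only.

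Compared with withdrawal, keeping everyone changes t-test power by 60 − 70 = −10 to 75 − 70 = about +5 percentage points from these rounded figures (+4 before rounding).

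**The case against.** The strongest reply is that the investigators do not mean the clause literally. Complications are an objective, are recorded from surgery onwards and are compared between groups, which suggests loose drafting. The clause also ends in a stray repeated fragment. Care follows routine practice, so clinical follow-up would probably continue. All of this is fair, and it makes the intent uncertain. It does not supply a sentence that allows scores after withdrawal to be collected or used, and it leaves the choice open until results are known.

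Second, the bias is unquantified. This stands. On the broad reading, many events would be minor or unrelated, with an average loss at 24 months near zero and little bias. The losses of 10 to 20 points describe serious shoulder complications. Even then, 1 to 4 points is at most half of the 8-point threshold.

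Third, the case for unequal complications is thin. The Introduction's statements are theoretical or conditional, and the humeral configuration of the two trial implants is not stated. This also stands: a difference is plausible but not established.

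Fourth, the allowance of 4 per arm is one reading. The sample-size paragraph attaches the 20% loss first to 34 patients and then gives 42.

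Fifth, retention can cost power, as the working shows. The case for it rests on bias.

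**Conclusion.** The concern holds and must be fixed. The plan contains a mandatory, unqualified rule that reaches the primary variable, and no other section retains the data, defines who is analysed or handles missing scores. Followed as written, with withdrawn patients left unscored, it replaces the randomised comparison with one selected on an outcome of surgery.

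Confidence is high about the rule and the omission. It is not high about any amount of bias: direction and size are unknown, 1 to 4 points is an illustration under assumed risks and losses, and zero is possible. The seriousness comes from the rule's reach and from scores that cannot be recovered if not collected.

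**What to change.** 1. Delete the adverse-event clause as a ground for leaving the study. State that an adverse event does not end follow-up or data collection. This concerns study data only and changes no clinical care.
2. State that all randomised patients are followed to 24 months unless they withdraw consent, and are analysed in their randomised arm, including those with complications or revision.
3. Report deaths, consent withdrawals and other losses by arm.
4. Add one sensitivity analysis for missing 24-month scores: show how far the arm difference moves if missing patients in one arm scored 8 points below those observed. With 4 of 21 missing this is 4/21 × 8 = 1.5 points. Repeating it at 20 points (4/21 × 20 = 3.8) would cover the larger losses illustrated above.
5. Reconcile the Withdrawal Criteria with the Objective, the Procedure, the complication analysis and the adverse-event row of the schedule.
6. Reconcile the visit times. The Statistical Analysis section has "different evaluation times of the study (1, 3, 6, 12, 18 and 24 months"), while the Procedure section has "Three, Six, Twelve and 24 months after surgery". The Period of Study table shows closure at 12 months, before the primary endpoint. Its columns do not line up in the available copy, so check this against the source table.

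The cost is wording, plus 24-month scores for patients with events at an assessment already planned. The power cost or gain is as shown in the working.
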